1.2 STUDY DESIGN

Study WA42293 is a Phase III, randomized, double-blind, placebo-controlled, pivotal clinical trial designed to confirm the efficacy and safety of zinpentraxin alfa in the treatment of IPF patients with or without concurrent treatment with pirfenidone or nintedanib.

Approximately 658 patients will be randomly assigned on a 1:1 basis to treatment with zinpentraxin alfa at a dose of 10 mg/kg or matched placebo on Days 1, 3, and 5, then one infusion every 4 weeks (Q4W) for 48 weeks. Patients will be evaluated for study eligibility during a screening period of up to 4 weeks. Study treatment will be administered by intravenous (IV) infusion over 50–70 minutes every 4 weeks. If any infusions are missed, repeat loading doses will be required at the next scheduled visit (three doses administered on alternate days). During the placebo-controlled treatment period (defined as Day 1 to Week 52), patients will continue to receive blinded study treatment every 4 weeks to Week 48 and have a final assessment visit at Week 52.

[figure not shown]
This study will enroll approximately 658 patients globally across all sites. Enrollment will be globally competitive. After completion of the global enrollment phase, additional patients may be enrolled in an extended China enrollment phase at sites in mainland China, Hong Kong, and Taiwan. The global population will include all patients enrolled during the global enrollment phase and the China subpopulation will include all patients enrolled at sites in mainland China, Hong Kong, and Taiwan (i.e., during both the global

enrollment phase and the extended China enrollment phase). Separate analyses will be performed for the global population and the China subpopulation (see Section 4.7.6 for China subpopulation analyses).

Following participation in this study, patients may be eligible to participate in a separate open-label extension (OLE) study (Study WA42294) to receive treatment with zinpentraxin alfa and further study assessments. Patients who do not enroll in the OLE study will be followed up for an additional 4 weeks (to Week 56, for safety monitoring). The OLE study will also consist of a long-term survival cohort, where patients who do not want further study assessments or treatment can enroll (for long-term collection of survival data only).

The study schema is shown in Figure 1.

Figure 1 Study Schema

IV=intravenous; OLE=open-label extension; Q4W=once every 4 weeks.

^a Patients will have a final assessment visit at Week 52 (4 weeks after the final study drug infusion). For patients enrolling into the OLE study, this will also be their end of study visit.

^b Patients who do not enroll in the OLE study will have their final assessment visit at Week 52, followed by an end of study visit at Week 56 (8 weeks after the final study drug infusion).

1.2.1 Treatment Assignment and Blinding

1.2.1.1 Treatment Assignment

This is a randomized, double-blind study. After initial written informed consent has been obtained, all screening procedures and assessments have been completed, and eligibility has been established for a patient, the study site will obtain the patient's identification number and treatment assignment from an interactive voice or web-based response system (IxRS).

Patients will be randomly assigned to one of two treatment arms: zinpentraxin alfa or placebo. Randomization will occur in a 1:1 ratio through use of a permuted block randomization method to ensure a balanced assignment to each treatment arm and will be stratified as follows:

- Concurrent use of nintedanib treatment versus pirfenidone treatment versus no concurrent treatment
- Geographic Region (China [including Hong Kong and Taiwan, if applicable], North America [United States and Canada], Europe [including eastern Europe], Latin America, and Rest of World [including east Asia, Australia, and New Zealand])

The randomization method implemented in the China extension cohort will be the same as that implemented in the global population, except for the stratification factor for geographic region.

1.2.1.2 Blinding

Patients and all study site personnel will be blinded to treatment assignment during the study. The Sponsor and its agents will also be blinded to treatment assignment, with the exception of individuals who require access to patient treatment assignments to fulfill their job roles during a clinical trial. These roles include the unblinding group responsible, clinical supply chain managers, sample handling staff, operational assay group personnel, IxRS service provider, the independent data coordinating center (iDCC) and independent Data Monitoring Committee (iDMC) members.

While pharmacokinetic (PK) and immunogenicity samples must be collected from patients assigned to the comparator arm to maintain the blinding of treatment assignment, PK and anti-drug antibody (ADA) assay results for these patients are generally not needed for the safe conduct or proper interpretation of the study data. Laboratories responsible for performing study drug PK and ADA assays will be unblinded to patient treatment assignments to identify appropriate samples for analysis. PK samples from patients assigned to the comparator arm will not be analyzed for study drug PK concentration except by request (e.g., to evaluate a possible error in dosing). Plasma concentration (i.e., baseline, predose PK samples) to measure the endogenous level of human pentraxin-2 (hPTX-2) may be analyzed from all patients including patients from the comparator arm. Baseline immunogenicity samples will be analyzed for all patients. Post-baseline immunogenicity samples from patients assigned to the comparator arm will not be analyzed for ADAs except by request.

If unblinding is necessary for a medical emergency (e.g., in the case of a serious adverse event (AE) for which patient management might be affected by knowledge of treatment assignment), the investigator will be able to break the treatment code by contacting the IxRS. The investigator is not required to contact the Medical Monitor prior to breaking the treatment code; however, the treatment code should not be broken except in emergency situations.

Zinpentraxin alfa is a human recombinant form of a naturally occurring regulatory protein, and there is no known antidote to this protein in the event of a safety event. If the investigator wishes to know the identity of the study drug for any reason other than a medical emergency, he or she should contact the Medical Monitor directly.

The investigator should document and provide an explanation for any non-emergency unblinding. If the Medical Monitor agrees to patient unblinding, the investigator will be able to break the treatment code by contacting the IxRS.

As per health authority reporting requirements, the Sponsor's Drug Safety representative will break the treatment code for all serious, unexpected suspected adverse reactions (see Section 5.8 in Protocol) that are considered by the investigator or Sponsor to be related to study drug. The patient may continue to receive treatment, and the investigator, patient, and Sponsor personnel, with the exception of the Drug Safety representative and personnel who must have access to patient treatment assignments to fulfill their roles (as defined above), will remain blinded to treatment assignment.

1.2.2 Central Review and Adjudication

Central review and adjudication will be performed for clinical and safety data as needed, prior to the efficacy or safety analyses. The membership and procedures of each central review or adjudication will be detailed in a charter or requirements document.

1.2.2.1 Pulmonary Function Tests

Standardized spirometry equipment and procedure guidelines will be provided to all study sites. As some pulmonary function tests (PFTs) are considered aerosol-generating procedures, additional precautions to reduce potential spread of infection should be taken in accordance with local guidance. Spirometry will be performed according to American Thoracic Society (ATS) / European Respiratory Society (ERS) guidelines (as referenced in the PFT manual) as per the schedule of activities (see Appendix 1 of the protocol). Details on PFT procedures are available in the PFT manual. PFT data will be sent for central review.

Carbon monoxide diffusing capacity (DL_{CO}) will be measured according to ATS/ERS guidelines (as referenced in the PFT manual). DL_{CO} will be performed using local equipment, as this will not be provided to study sites.

Acceptability of the spirometry and DL_{CO} data from the computerized system (including screening assessments) will be determined by over-readers blinded to study drug treatment (comprising graphic representations of the maneuvers as well as numerical results). Calculations for the reproducibility of the acceptable maneuvers will be performed and reviewed centrally by over-readers blinded to study drug treatment. Only acceptable spirometry and DL_{CO} data will be used.

The screening spirometry and/or DL_{CO} sessions may be repeated once, if the initial session is rejected by the over-reader. This is the only session during the study that may be repeated. In extenuating circumstances, one further spirometry and/or DL_{CO} session may be attempted after discussion with the Medical Monitor. No more than three spirometry and/or DL_{CO} sessions should be performed during the screening period. Repeat sessions are only permitted following rejection of previous sessions by the over-reader.

1.2.2.2 High-Resolution Computed Tomography

Pulmonary high-resolution computed tomography (HRCT) scans will be reviewed during screening to confirm the IPF diagnosis. Good-quality standard of care scans obtained ≤ 12 months prior to screening and in accordance with study image acquisition guidelines can be used for eligibility determination. If scans meeting these conditions are not available, an HRCT scan may be conducted during screening. HRCT scans will be reviewed first by the site radiologist and/or investigator to assess for eligibility.

If the site determines that the patient's HRCT meets IPF diagnostic criteria as specified in the Protocol, the HRCT scans will be sent for central review to confirm eligibility. The blinded central review radiologists will evaluate screening images in accordance with the 2018 Clinical Practice Guidelines by ATS, the ERS, Japanese Respiratory Society (JRS), and the Latin American Thoracic Society (ALAT) ([Raghu et al. 2018](#)). Final eligibility will be determined by the central review assessments, inclusive of lung biopsy, if available.

1.2.2.3 Lung Biopsy

Lung biopsies are not required for eligibility into the study. Patients who have undergone a lung biopsy (including cryobiopsy) to aid in the diagnosis of IPF, should have slides sent for central review assessment to confirm eligibility in accordance with the ATS/ERS/JRS/ALAT Clinical Practice Guideline ([Raghu et al. 2018](#)). The central review pathologists will evaluate submitted slides for usual interstitial pneumonia (UIP) pattern. The histopathologic assessment criteria are outlined in the Protocol.

1.2.2.4 Assessment of Acute Exacerbations of IPF, Hospitalizations for Respiratory Causes, and Deaths (Adjudicated Events)

An independent, blinded Clinical Adjudication Committee will be convened to review all available data for all potential cases of acute or suspected exacerbations of IPF, hospitalizations for respiratory causes, and all deaths. This Clinical Adjudication Committee will be comprised of pulmonary disease physicians familiar with IPF exacerbations. A charter for the Clinical Adjudication Committee will provide further details. The Clinical Adjudication Committee will determine if the reported events meet the criteria of acute or suspected exacerbation of IPF, hospitalization for respiratory causes, and deaths (including deaths related specifically to respiratory causes) as defined in the charter.

1.2.2.5 Assessment for Suspected Anaphylaxis

Assessment of potential anaphylaxis will be conducted at every infusion per the clinical criterion for diagnosing anaphylaxis as described by Sampson et al. (2006) NIAID/FAAN.

All potential anaphylaxis cases reported by investigators to the Sponsor will be subsequently submitted for adjudication to a blinded Anaphylaxis Adjudication Committee, composed of external experts in allergic diseases. The committee will assess whether the reported event is a true anaphylaxis event (based on Sampson's criteria) and whether the reported anaphylaxis event is causally related to study treatment.

If a patient has signs or symptoms of an anaphylactic or serious hypersensitivity reaction (including events deemed to have met the criteria as described by Sampson according to the blinded Anaphylaxis Adjudication Committee), administration of the study drug must be discontinued permanently.

Further details will be provided in the Anaphylaxis Adjudication Charter.

1.2.3 Data Monitoring

An iDMC will be established to review safety data from this study, thereby better ensuring the safety of study participants. If appropriate, the iDMC may also evaluate benefit and risk by reviewing relevant efficacy data together with safety data during the scheduled iDMC meetings. Consistent with US Food and Drug Administration (FDA) recommendations ([FDA Guidance for Industry, Establishment and Operation of Clinical Trial Data Monitoring Committees 2006](#)), the iDMC will be constituted of independent clinician's expert in the field of IPF and clinical research and a statistician. A formal charter will be established for the conduct of the iDMC. The Committee is planned to review the safety data in an unblinded manner. The iDMC may also review other data (e.g., PK) according to local health authority requirements. Details regarding the iDMC data evaluation will be specified in the iDMC charter.

2. STATISTICAL HYPOTHESES AND SAMPLE SIZE DETERMINATION

2.1 STATISTICAL HYPOTHESES

The following statistical hypotheses will be tested to demonstrate superiority of zinpentraxin alfa plus standard of care treatment as needed (excluding lung transplantation) compared with placebo plus standard of care treatment as needed (excluding lung transplantation), on lung function for the primary efficacy endpoint:

Null hypothesis H0: the mean change from baseline at Week 52 in FVC mL for patients in the placebo arm is the same as the mean change from baseline at Week 52 in FVC mL for patients in the respective zinpentraxin alfa arm.

Alternative hypothesis H1: the mean change from baseline at Week 52 in FVC mL for patients in the placebo arm is not the same as the mean change from baseline at Week 52 in FVC mL for patients in the respective zinpentraxin alfa arm.

Similar statistical hypotheses will be tested for the key secondary efficacy endpoint: change from baseline at Week 52 in 6-minute walk distance (6MWD).

A fixed-sequence testing strategy will be used for statistical testing of first the primary endpoint then the secondary endpoints in a hierarchical manner to control the overall type I error rate at 0.05 two-sided. See Section 4 for details.

2.2 SAMPLE SIZE DETERMINATION

The purpose of this study is hypothesis testing regarding the effect of zinpentraxin alfa versus placebo.

2.2.1 Assumptions on Treatment Effects for Sample-Size and Power Calculations

The hypotheses on treatment effect-sizes used for sample-size and power calculations were based on the results of the placebo-controlled period of the PRM-151-202 study, summarized in Table 3.

Table 3 Results of the PRM-151-202 Study on Planned Primary and Key Secondary Endpoints

LS-Means for change from baseline at Week 28 (linear mixed effect models)				
Endpoint	Placebo (N=39) Mean (SE)	zinpentraxin alfa (N=77) Mean (SE)	Difference Mean (SE)	Standardized effect size
FVC (mL)	-242.3 (45.47)	-127.7 (32.86)	114.6 (56.10)	0.40
6MWD (meters)	-33.7 (10.52)	-0.20 (7.59)	33.5 (12.97)	0.51
FVC (% predicted)	-5.40 (0.96)	-2.50 (0.69)	2.80 (1.19)	0.46

6MWD=6-minute walk distance; FVC=forced vital capacity; SE=standard error.

The effect-sizes observed for the between-group differences in least-square means for change from baseline at Week 28 from the linear mixed effect models with random intercept and slope adjusted on stratum, were 114.6 mL for FVC mL (common standard deviation: 286.9, standardized effect-size: 0.40), 33.5 m for 6MWD (common standard deviation: 66.3, standardized effect-size: 0.51), and 2.80% for FVC % predicted (common standard deviation: 6.04, standardized effect-size: 0.46). A greater between group difference is expected at Week 52 in the current study, but a greater variability might also be observed at Week 52, due to the longer follow-up.

In the OLE of the PRM-151-202 study, where all patients received zinpentraxin alfa from Week 28 onwards, the Week 52 standard errors from the mixed model for repeated measures (MMRM) model allowed to compute corresponding standard deviations of 403.5 mL (FVC mL), 8.77% (FVC %predicted) and 82.3 m (6MWD) in patients who were initially randomized to zinpentraxin alfa, that are indeed larger than those at Week 28 (288.3 mL, 6.06% and 66.6 m respectively).

To avoid underestimating the power of the study and to enable the opportunity to explore the efficacy in relevant patient subgroups including baseline concomitant IPF medication use, smaller standardized effect-sizes than observed in study PRM-151-202 at Week 28 of 0.25 for FVC mL and FVC % predicted and 0.30 for 6MWD were used for the calculations. In addition, to investigate the impact of increased variability for studies of longer duration, the power for this calculated sample size was assessed in the following way: (a) using the placebo-controlled treatment differences observed at Week 28 as estimates for the Week 52 treatment effects and (b) using the Week 52 standard deviations for the initially randomized zinpentraxin alfa arm from study PRM-151-202, as estimates for the Week 52 common standard deviations. This was performed in order to confirm that the nominal power is at least 80% under these assumptions.

With a total of 658 patients (329 in each arm), the nominal power to detect a standardized effect size of 0.25 for FVC mL and FVC% predicted, using a two-sided type I error level of 0.05 is 0.89 and the nominal power to detect a standardized effect size of 0.30 on 6MWD using a two-sided type I error level of 0.05 is 0.97.

With a total of 658 patients (329 in each arm), the nominal power to detect an effect of 114.6 mL on FVC mL with common standard deviation of 403.5 (standardized effect size of 0.28) using a two-sided type I error of 0.05 is 0.95. The nominal power to detect an effect of 33.5 meters on 6MWD with common standard deviation of 82.3 (standardized effect size of 0.41) using a two-sided type I error level of 0.05 is >0.99. For FVC% predicted, the nominal power to detect an effect of 2.80% with common standard deviation of 8.77 (standardized effect size of 0.32) using a two-sided type I error of 0.05 is 0.98.

2.2.3 Sample Size for the China Subpopulation

This study will initially enroll approximately 658 participants across all sites during the global enrollment phase. After completion of the global enrollment phase, additional participants may be enrolled in an extended China enrollment phase at sites in China, Hong Kong and Taiwan to ensure a total enrollment that is sufficient to support registration in China. The global population will include all participants enrolled during the global enrollment phase (including participants enrolled at National Medical Products Administration (NMPA)-recognized sites during that phase), and the China subpopulation will include all participants enrolled at NMPA-recognized sites (during both the global enrollment phase and the extended China enrollment phase).

3. ANALYSIS SETS

The analysis populations presented in this section are based on patients enrolled during the global enrollment phase of the study and will not include the China extension, unless otherwise specified. The analysis plan for the China extension is presented in Section 4.7.6.

The analysis populations are defined in Table 5.

Table 5 Analysis Populations

Population	Definition
Randomized	All randomized patients
Full analysis set	All randomized patients who received at least one administration (full or partial dose) of study drug and will use the grouping according to the treatment assignment at randomization.
Safety-evaluable	All randomized patients who received at least one administration (full or partial dose) of study drug and will be grouped according to the actual treatment received.
Pharmacokinetic-evaluable	All randomized patients who received at least one administration (full or partial dose) of zinpentraxin alfa and have at least one evaluable postdose PK sample that is above the LLOQ.
Immunogenicity-evaluable	All randomized patients with at least one postdose ADA assessment and will be grouped according to treatment received or, if no treatment is received prior to study discontinuation, according to treatment assigned.
Biomarker-evaluable	All randomized patients who received at least one administration (full or partial dose) of zinpentraxin alfa and have genetic data to enable assessment of MUC5B status. The analysis will group patients according to treatment actually received.

LLOQ = lower limit of quantification; MUC5B = mucin 5B; PRO = patient-reported outcomes.

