Exploratory Efficacy Objective	Corresponding Endpoints

 • To evaluate the efficacy of zinpentraxin alfa plus SOC treatment as needed compared with placebo plus SOC treatment as needed 	
 • Absolute change from baseline at Week 52 in FVC% predicted and FVC (mL), by baseline concomitant medication stratum • Absolute change from baseline at Week 52 in FVC% predicted and FVC (mL), by mucin 5B (MUC5B) risk allele positive or negative status • Absolute change from baseline at Week 52 in 6MWD (m), by baseline concomitant medication stratum • Proportion of patients who progress on the UCSD-SOBQ, as indicated by an increase in score of 10 points or greater • Proportion of patients who progress on the SGRQ total score, as indicated by an increase in score of 7 or greater • Change from baseline to Week 52 in SGRQ Individual Domains (Symptoms, Activity, and Impacts) Score • Proportion of patients who progress on the SGRQ Symptoms Domain, as indicated by an increase in score of 8 or greater • Proportion of patients who progress on the SGRQ Activity Domain, as indicated by an increase in score of 5 or greater • Proportion of patients who progress on the SGRQ Impacts Domain, as indicated by an increase in score of 7 or greater • Absolute change from baseline at Week 52 in quantitative imaging analysis parameters of HRCT scan of the thorax • Length of hospital stay for respiratory-related hospitalizations • Total time in intensive care units due to respiratory causes • Unscheduled outpatient clinic/urgent care/emergency room utilization related to respiratory events

	
 • Number of acute exacerbations during the 52 weeks; as determined by the Clinical Adjudication Committee • Survival as measured by IPF-related mortality • Survival as measured by respiratory-related mortality • Disease progression and subsequent start of oxygen supplementation • Change in PFT parameters (FVC, DL_{CO}) or 6MWD from baseline at Week 52 between SARS-CoV2 antibody positive compared with negative patients (present at baseline) • Change in PFT parameters (FVC, DL_{CO}) or 6MWD from baseline at Week 52 in patients who develop SARS-CoV2 antibodies during treatment (not present at baseline) • Absolute change from baseline at Week 52 in FVC (mL) by selected countries
Safety Objective	Corresponding Endpoints

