The primary efficacy objective is to evaluate the effect of zinpentraxin alfa plus standard of care (SOC) treatment as needed compared with the matching placebo plus SOC treatment as needed on disease progression at Week 52, regardless of changes to the initial treatment regimen (including randomized drug and any associated treatment) and in the absence of lung transplantation. The primary estimand is the difference in mean absolute change from baseline at Week 52 in forced vital capacity (FVC) mL between zinpentraxin alfa and placebo treated patients. The primary estimand is further described by the following attributes:

- Population: adults diagnosed with IPF who meet the inclusion/exclusion criteria presented in Section 4.1 of the protocol.
- Treatment: study drug (zinpentraxin alfa or placebo) as randomized, in combination with any background or additional treatment (i.e., zinpentraxin alfa or placebo taken alone or as an add-on to SOC with pirfenidone or nintedanib, dosed as required) including all changes in SOC treatment and all other additional treatments, with the exclusion of lung-transplantation.
- Variable: absolute change from baseline at Week 52 in FVC mL.
- Population-level summary measure: between randomized treatment difference in mean change from baseline at Week 52 in FVC mL.
- Intercurrent events:
 - Change to initial treatment regimen: The treatment effect of interest is irrespective of changes to the initial treatment regimen, which include changes to study drug (including treatment discontinuation), changes to standard of care, and the use of prohibited medication. Therefore, all data collected after changes to the initial treatment regimen will be included in the analysis. Any data missing after changes to the initial treatment regimen will be assumed to be missing at random (MAR). A sensitivity analysis described in Section 4.3.3.1 will assess the impact of assuming that data missing after treatment discontinuation is MAR.

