4.1 GENERAL CONSIDERATION

The efficacy endpoints comprise one primary endpoint (FVC [mL]), one key secondary endpoint (6MWD [m]), a series of other secondary endpoints and other exploratory endpoints. All efficacy analyses will be performed on the FAS population, unless otherwise specified. Participants will be analyzed according to the treatment assigned at randomization by IxRS. Significance testing of the primary and secondary endpoints will account for multiplicity and control family-wise type I error, which is fixed at 0.05 two-sided. All safety analyses will be performed in the safety-evaluable population, unless otherwise specified. Participants will be analyzed according to the treatment they actually received.

In safety analyses, all deaths are included, from all sources, regardless of completeness of death date; participants who died with only a partial death date available will be included. In efficacy analyses, death data from adjudication will be used. If the death date is only partially available, the missing part of the date will be imputed.

For hospitalization in efficacy analyses, the adjudicated date of hospitalization will be used and a partial date will be imputed using the same approach as for death.

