4.3.2 Main Analytical Approach for Primary Endpoint

Descriptive statistics for the raw values at each visit and the change from baseline at each visit through Week 52 in FVC mL will be computed by treatment group for the FAS population.

The comparison of zinpentraxin alfa with placebo will be carried out via a linear mixed (random coefficient) model at a 0.05 two-sided significance level. Each subject's vector of responses is independent of the other subjects, and within-subject responses are correlated.

The statistical model can be written as follows:

$$Y_{ij} = (\beta_0 + \beta_{0i}) + (\beta_1 + \beta_v Trt_i + \beta_{1i}) * t_{ij} + \beta_s Sex_i + \beta_a Age_i + \beta_h Height_i + \beta_c StrataC_i + \beta_r StrataR_i + \epsilon_{ij}$$

where

- Y_{ij} is the FVC (mL) value for subject i at visit j (including baseline);
- β_0 and β_1 are the intercept and the slope;
- β_{0i} and β_{1i} are the random subject effects for intercept and slope;
- $Trt_i = 0$ if subject i is in the Placebo group and $Trt_i = 1$ if subject i is in the zinpentraxin alfa group;
- β_v is the coefficient for the interaction term of treatment effect and assessment time;
- t_{ij} is the assessment time (continuous in days) for subject i at visit j ;
- β_s , β_a and β_h are the coefficients for subject specific demographic variables;
- Sex_i , Age_i , and $Height_i$ are the sex (male as the class of reference), baseline age (years) and baseline height (cm) for patient i ;
- β_c and β_r are the coefficients for subject specific stratification variables;
- $StrataC_i$ and $StrataR_i$ are the stratification factors on concurrent IPF treatment (no concurrent IPF treatment as the class of reference) and region (Rest of World as the class of reference) for subject i ;
- ϵ_{ij} is the within-subject random error for subject i at visit j ;
- β_{0i} and β_{1i} are assumed to have a multivariate normal distribution with mean 0 and unstructured covariance matrix;
- ϵ_{ij} are assumed to be independent and normally distributed with mean 0 and variance σ_ϵ^2

If there are convergence problems with the model, the following covariates will continue to be removed from the model (in this order) until convergence is met (1) stratification factor for region, (2) stratification factor for concurrent IPF treatment (3) age, sex, and height. If the model still fails to converge, a random intercept model will be used (no random slope).

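### SAP Table 5 defines the biomarker-evaluable (MUC5B) set by receipt of zinpentraxin alfa instead of study drug, so it holds no placebo-only patients and its link to the one MUC5B endpoint is unclear

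*SAP*

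**What the plan says.** Table 5 in SAP Section 3 defines six analysis populations. The biomarker-evaluable row takes randomized patients who "received at least one administration (full or partial dose) of zinpentraxin alfa and have genetic data to enable assessment of MUC5B status". It then adds: "The analysis will group patients according to treatment actually received".

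The FAS row requires a dose of "study drug and will use the grouping according to the treatment assignment at randomization". The safety-evaluable row also requires a dose of study drug. SAP 1.1 states the treatment attribute of the primary estimand as "study drug (zinpentraxin alfa or placebo) as randomized", so study drug covers both arms.

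The SAP has one MUC5B endpoint: absolute change at Week 52 in FVC% predicted and FVC (mL) by MUC5B risk-allele status (SAP 1.1, Table 1, and SAP 4.5). Table 1 places it under the exploratory efficacy objective: "To evaluate the efficacy of zinpentraxin alfa plus SOC treatment as needed compared with placebo plus SOC treatment as needed".

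For populations, SAP 4.1 says: "All efficacy analyses will be performed on the FAS population, unless otherwise specified". For grouping, it says: "Participants will be analyzed according to the treatment assigned at randomization by IxRS". SAP 4.5 does not state which set the MUC5B endpoint uses. SAP 4.7.4 defers exploratory biomarker analyses to a separate Biomarker Analysis Plan, which is not among the documents.

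**The concern.** The set is built around MUC5B genotype, and the only endpoint that uses that genotype compares drug with placebo. A set entered only through a dose of zinpentraxin alfa has no comparator.

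This matters because Protocol 6.9 foresees genotype-outcome comparisons that look for prognostic or predictive properties, and Protocol 3.3.4 names MUC5B among the potential predictors of how fast IPF progresses. Among drug recipients alone, a difference in FVC decline between allele groups could be pure prognosis. Only a comparison of the drug effect between allele groups, which needs placebo patients in each, speaks to prediction.

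There is also a mismatch in grouping. The biomarker row groups patients as treated, while SAP 4.1 analyzes efficacy as randomized. A programmer who took Table 5 as the specification for the MUC5B endpoint would get both the population and the grouping wrong.

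**Working it through.** No figure in the plan depends on this definition, so there is none to reproduce. The check sets the sections side by side, with a count and an identifiability argument.

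**1. Who can enter.** The design is 1:1 with 658 patients, 329 per arm (SAP 2.2.1). Let g be the share of patients with a usable genotype. The documents do not give g, so it is an assumption.

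- As written: at most 329 × g zinpentraxin alfa patients and 0 placebo-only patients, at any g. A patient randomized to placebo could enter only after receiving drug in error, and would then be grouped as active.
- With study drug in place of zinpentraxin alfa: about 329 × g per arm.

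| Assumed g | Placebo patients as written | Per arm after correction |
|---|---|---|
| 1.0 | 0 | 329 |
| 0.9 | 0 | about 296 |
| 0.7 | 0 | about 230 |
| 0.5 | 0 | about 164 |

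In practice g is below 1. Under Protocol 4.5.15, DNA collection for sequencing depends on site approval and excludes mainland China. The Protocol Appendix 3 schedule for China, Hong Kong and Taiwan lists no DNA sample.

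**2. Whether sampling explains the restriction.** It does not. Protocol Appendix 2 schedules DNA at screening, and Protocol Appendix 10 says screening ends at randomization. Genotype availability is therefore not tied to arm. The PK-evaluable row has the same zinpentraxin alfa wording, but there it fits, because SAP 1.2.1.2 says comparator PK samples are not assayed for drug except by request. Nothing comparable applies to genotype.

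**3. What the row's second sentence does.** If every member received zinpentraxin alfa, grouping by treatment received produces one group. The sentence is then redundant, which suggests the author had two groups in mind.

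**4. What would happen if the set were used.** SAP 4.5 sends exploratory FVC endpoints to the methods of SAP 4.3.2: "The comparison of zinpentraxin alfa with placebo will be carried out via a linear mixed (random coefficient) model". In that model the population slope is β1 + βv × Trt, with Trt = 0 for placebo and 1 for zinpentraxin alfa. If Trt = 1 for everyone, the slope is β1 + βv. Only the sum is estimable, and βv, the treatment effect on slope, is not. This holds within each MUC5B stratum and at any g. The FVC% predicted model drops age, sex and height but keeps the same treatment term, so the argument carries over.

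**5. Whether the set is used.** Outside Table 5, the SAP does not name it. SAP 4.2 lists populations to be summarized and omits it; SAP 4.5 and 4.7.4 do not mention it. Section 4.1 counts exploratory endpoints among the efficacy endpoints and defaults them to the FAS as randomized. On the current text, FVC by MUC5B status can be compared between arms in FAS patients with a genotype.

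**The case against.** The strongest reply is that the row does no harm. No SAP analysis is assigned to the set, and the Section 4.1 default already gives the MUC5B endpoint the right population and grouping. The identifiability argument bites only if someone fits the model in a set that no section tells them to use. Any further harm depends on a Biomarker Analysis Plan that cannot be seen here, and Protocol 6.9 says only that genotype-outcome comparisons may be made. Redundant grouping language is also not proof of error: Protocol 6.7 groups the PK population by treatment received as well.

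Most of this stands, and it limits the point. A reader might infer that the MUC5B objective cannot be met, or that the placebo arm is lost from the MUC5B analysis. The documents support neither. There is no separate MUC5B objective, only one endpoint under the general exploratory objective, and the FAS route to it is open.

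The reply does not make the row correct. The FAS default yields where something else is specified, and a dedicated MUC5B set that states how its patients are grouped can be read as that exception. The two routes differ in population and in grouping, and SAP 4.5 does not choose between them. SAP Appendix 1, which lists the major changes from the protocol, records no move to a drug-only MUC5B analysis.

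**Conclusion.** The concern holds as a wrong set definition with an unclear link to one exploratory endpoint. Severity is minor. As written, the set holds no placebo-only patients. The treatment effect by MUC5B status would be inestimable only if this set, or a Biomarker Analysis Plan that adopts it, were used for that comparison.

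The conclusion rests on a literal reading of the row and on study drug having the meaning given in SAP 1.1. That the wording is a slip, perhaps carried over from the PK-evaluable row, is likely but cannot be confirmed from the documents. The endpoint lies outside the fixed testing sequence, so primary and secondary tests, alpha and power are unaffected.

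**What to change.** In Table 5, define the biomarker-evaluable set as FAS patients (at least one dose of study drug, either arm) with an evaluable MUC5B genotype, grouped as randomized for efficacy in line with SAP 4.1. In SAP 4.5, add a sentence naming this set for FVC by MUC5B status. Changing only the drug name would leave the as-treated grouping in conflict with Section 4.1, so both parts of the row need revision. Check that the Biomarker Analysis Plan uses the corrected definition.

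The cost is one table row and one sentence. No new samples or assays are needed, because the planned DNA sampling does not depend on arm.
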